Diet could extensively affect the environment of human intestine, which harbors trillions of microbes, commonly referred to as the “intestinal microbiota”, and “microbiome” (the collection of microbes and all the genes and functionalities they encode [8]). Numerous studies have suggested that the intestinal microbiota is closely associated with overall human health [9, 10]. More importantly, the human gut microbiome is a rich pool of potential biomarkers that have been previously shown to be associated with disease states including IBD [11, 12]. Microbiome-based stratification strategies of patients groups have been widely employed to guide dietary intervention studies [13]. Recently, a low-fat, high-fiber diet has been found to reduce inflammatory markers and alter the microbiome in patients with mild UC or UC in remission [14]. Another similar study demonstrated that a fiber-based prebiotic resulted in less abdominal pain and cramping in UC patients [15]. This indicates that increasing dietary fiber intake could be beneficial for maintaining periods of remission or improving clinical outcomes in patients with UC. Furthermore, short chain fatty acids (SCFAs) such as butyrate are produced by intestinal bacteria when they break down dietary fibers and these are considered beneficial for gut health. In a pilot study, it was demonstrated that UC patients could take a fiber-rich diet to increase the fecal butyrate level [5]. However, response to a treatment differs drastically between subjects, with some patients entering remission (responder), while others fall or remain into relapse (non-responders). The reasons for this inconsistent response between subjects remain speculative but may be the result of differences in the personal gut microbiota composition [16].

[figure not shown]

Figure 1 Existent tipping point in ecosystem. (adapted from reference 17 and 18.)

Looking from an ecological perspective, ecosystems are generally consisting of alternative stable states that are resilient to (minor) perturbations. Changing from one stable state into another stable state needs a strong perturbation in which a tipping point needs to be crossed (Figure 1) [17, 18]. For example, both deserts and rainforests are stable states, and only a drastic perturbation, like deforestation, allows a rainforest to cross a tipping point to become a desert, and similarly, it will need a lot of effort to have it return again from a desert into a rainforest in

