4.2 Inclusion criteria

1. Male and female subjects aged 18 to 65 years*
2. Body Mass Index (BMI) between 18 and 30 kg/m² (self-reported)
3. Ulcerative Colitis confirmed via previous endoscopy and histology
4. Mild active UC as defined by P-SCCAI score of 3 to 5 (range 0 to 19)
5. Frequent relapse (at least one exacerbation in the last two years)
6. No known allergy to any components of the study product (self-reported)
7. Signed informed consent
8. Stable UC medication defined as no switch to other medication or no dose change
9. Mobile phone on which apps (used for questionnaires) can be downloaded (iOS version 9 and newer, Android version 4.4 and newer. Phones manufactured after 2013 are usually suitable)
10. Stable dietary pattern during the study

* We only include adults (age 18-65) as previous studies have shown that adolescent and elderly microbiota as well as UC presentation in adolescents can be different from adults[32, 33].

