4.4 Sample size calculation

The primary objective of the trial is to validate the prediction that a higher response (lower mean P-SCCAI score) is induced at T= 8 weeks by the prebiotics intervention in mild UC patients with low Bacteroidetes levels (predicted responders), but not in those with high Bacteroidetes levels (predicted non-responders) in their gut. Mild UC is defined as a P-SCCAI score of 3 to 5. According to an extensive study regarding UC disease activity conducted in the Netherlands, mild UC patients have a P-SCCAI score of 3.5 ± 0.5 (Mean \pm standard deviation (SD)), and patients in remission score at 1.0 ± 0.33 (Mean \pm SD)[34, 35].

In a series of germinated barley foodstuff (GBF) intervention studies, 10 mild to moderately active UC patients received 30 grams of GBF (equals to 10 grams fiber) daily for 4 weeks [4], and researchers found a significant decrease in clinical activity index scores. In a later study, another group of 11 mildly to moderately active UC patients consuming 20-30 grams of GBF (equals to 6.66-10 g fiber) daily for 4 weeks showed similar results, with decreases in clinical activity index scores [28].

Based on two-sided statistical testing for unpaired continuous data, an $\alpha=0.05$ (chance on type-I error) and $\beta=0.10$ (chance on type-II error), and assuming a 20% difference of mean P-SCCAI score between predicted responders with prebiotics and predicted non-responders with prebiotics, it was calculated that at least 11 subjects per group are needed for the primary outcome P-SCCAI ($\mu_1=3.5$; $SD_1=0.5$; $\mu_2=2.8$). According to previous trials on prebiotics on IBD patients, a 20% of drop-out rate is commonly seen. Given that the intervention duration is 8 weeks long, followed by a 1 year follow-up, higher dropout rate (30%) is expected. To compensate for a 30% drop-out rate, 15 subjects per group are needed.

To reach inclusion of 30 predicted responders and 30 predicted non-responders, we made an estimate how many subjects we need to screen based on the earlier obtained microbial composition of stool samples from UC patients in the Ede area. Around 50% of these subjects were categorized as low Bacteroidetes subjects (predicted responders) and while 17% of them as high Bacteroidetes subjects (predicted non-responders). To include these responders we will need to screen 177 mild UC patients.

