8.4.1 Specific criteria for withdrawal

A subject will be withdrawn from the study in the case of serious gastro-intestinal complaints or an exacerbation of UC reported by the subjects (such as continuous diarrhea or constipation, bloating, abdominal pain).

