10.2 Secondary study parameter(s)

Response over time

To assess the response over time, data of mean P-SCCAI score within each arm at T = 0, 4, 8, 12 and 60 weeks will be obtained. Comparisons will be made between groups (as done for T = 8 for the primary study parameter) as well as within subjects over time. With P-SCCAI score ≤ 2 being regarded as clinical remission, and a decrease in the P-SCCAI score by more than two points from baseline being regarded as clinical response, we will determine whether subjects have reached clinical remission and/or showed a clinical response over time.

To assess the response within each subject (clinical remission and/or clinical response) over time, data of sum P-SCCAI score within each subject at T = 0, 4, 8, 12 and 60 weeks will be obtained. For comparative analyses between baseline and intervention, the parametric paired sample T-test or the non-parametrical Kruskal-Wallis or Mann-Whitney

U test will be used, depending on the distribution of the samples. Differences between treatments before and after supplement intake will also be analysed by linear mixed models for repeated measures, using “treatment” [prebiotics/placebo], “responding” [responders/non-responders], “time point” [0, 4, 8, 12 and 60 weeks] and “treatment x responding x time point” as fixed effects and subject as random effect. Clinically relevant variables such as BMI, age, sex, and medication use will be taken into account.

Mucosal inflammation

Fecal calprotectin data will be analysed in the same manner as described above (Response over time).

GI complaints:

Data from GSRS will be computed into scores, and the score of each item will be pooled together as the sum score, and the score of each item within each domain will be pooled as well. All data will be analysed in the same manner as described above (Response over time). Differences over time within and between groups will be tested with mixed model analysis. Variables such as timepoint, group, age, sex will be taken into account.

Stool consistency and frequency

Average bowel movement per day and dynamic change on stool consistency will be calculated and collected. All data will be analysed in the same manner as described above (Response over time)..

Gut microbiota and SCFAs

Fecal SCFAs data will be analysed in the same manner as described above (Response over time)

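### The mixed model in Protocol 10.2 imposes one variance and one correlation on visits from week 0 to week 60, so its P-SCCAI standard errors are probably miscalibrated, mainly at week 60

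*Protocol*

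**What the plan says.** Protocol 10.2 (Response over time) states that "data of sum P-SCCAI score within each subject at T = 0, 4, 8, 12 and 60 weeks will be obtained". It plans between-group tests at each of these visits in the manner of the primary analysis, and paired or non-parametric tests against baseline. It then adds a linear mixed model for repeated measures. Treatment, predicted-response group, time point and their three-way product enter "as fixed effects and subject as random effect". Residual covariance, visit-specific variances, estimation method and degrees of freedom are not mentioned.

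The approach is carried to other outcomes, for example "Fecal calprotectin data will be analysed in the same manner as described above (Response over time", and likewise to SCFAs, GSRS, stool data and SIBDQ.

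On the spread of the score, Protocol 4.2 requires "Mild active UC as defined by P-SCCAI score of 3 to 5 (range 0 to 19". Protocol 4.4 reports that "mild UC patients have a P-SCCAI score of 3.5 ± 0.5" and "patients in remission score at 1.0 ± 0.33". No SD is given for weeks 4, 8, 12 or 60.

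**The concern.** A random subject intercept with independent residuals is compound symmetry: one variance at all five visits, and the same correlation between weeks 0 and 4 as between weeks 0 and 60. Two features of the design speak against it.

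- **Variance.** The entry window compresses the score at the start. Scores confined to 3, 4 and 5 have an SD of at most 1.0 (half at 3, half at 5), or 0.82 if the three values are equally common. Later scores are free to spread, and Protocol section 1 expects this, "with some patients entering remission (responder), while others fall or remain into relapse (non-responders".
- **Correlation.** Successive gaps are 4, 4, 4 and 48 weeks. One correlation for all pairs is hard to credit whatever the SDs.

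If the early variance is small and the late one large, the pooled value is too small for week 60 and too large for the early visits. At stake is the model-based reading of secondary objective 1 (response over time), above all the comparison one year after supplementation ends.

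**Working it through.** **The plan's own figure.** The protocol states no operating figure for the mixed model. Its only related figure is the week-8 sample size: n = 2 × (1.96 + 1.2816)² × (0.5/0.7)² = 2 × 10.51 × 0.510 = 10.7, so 11 per group. That reproduces Protocol 4.4 but does not bear on the covariance structure.

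**Is widening plausible on the protocol's figures?** Mix a share p of patients in remission (1.0 ± 0.33) with the rest at mild activity (3.5 ± 0.5):

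variance = p × 0.33² + (1 − p) × 0.5² + p(1 − p) × 2.5²

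- p = 0.2: 0.022 + 0.200 + 1.000 = 1.222, SD 1.11
- p = 0.5: 0.054 + 0.125 + 1.563 = 1.742, SD 1.32
- p = 0.8: 0.087 + 0.050 + 1.000 = 1.137, SD 1.07

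The SD is more than double 0.5 before any relapse is counted. Adding 10-30% relapsed patients (assumed mean 7, SD 2) takes it to 1.9-2.7.

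**What the model does.** Take complete data, equal arms and fixed effects that fit every arm-by-visit mean. The random-intercept fit then estimates the total variance by V, the average of the five visit variances, and the common covariance by C, the average of the ten pairwise covariances.

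- Between-arm difference at a visit: model SE / true SE = r = √V / SD at that visit (sample size cancels).
- Difference in change from baseline: r = √[2(V − C) / true variance of the change].
- Type I error at nominal 5% ≈ 2Φ(−1.96 r).

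**Between-arm difference at week 60** (all later SDs are assumptions):

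| SDs at weeks 0/4/8/12/60 | V | r | Type I error |
|---|---|---|---|
| 0.5/1.3/1.3/1.3/1.3 | 7.01/5 = 1.402 | 1.184/1.3 = 0.91 | 7.4% |
| 0.8/1.5/1.5/1.5/1.5 | 9.64/5 = 1.928 | 1.389/1.5 = 0.93 | 7.0% |
| 0.8/1.2/1.4/1.5/2.0 | 10.29/5 = 2.058 | 1.435/2.0 = 0.72 | 16.0% |
| 0.5/1.0/1.5/1.5/2.0 | 9.75/5 = 1.950 | 1.396/2.0 = 0.70 | 17.1% |
| all equal | SD² | 1.00 | 5.0% |
| 0.5/0.5/0.45/0.4/0.33 | 0.971/5 = 0.194 | 0.441/0.33 = 1.34 | 0.9% |

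Simulation of 20,000 null trials per setting (four arms of 15, complete data, Satterthwaite degrees of freedom) agrees. It gives 7.4-7.7%, 6.6-6.9%, 15.8-16.3%, 16.6-17.2%, 5.1-5.2% and 0.9-1.0% for the six rows, whichever of three correlation patterns is used. In the fourth row the closed form gives 0.6% at week 4 and 6.8% at weeks 8 and 12.

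**Change from baseline:**

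- SDs 0.5/1.0/1.5/1.5/2.0, correlation 0.6 per 8 weeks: r = 2.44, 1.33, 1.25 and 0.82 at weeks 4, 8, 12 and 60. Type I error is about 0%, 0.9%, 1.4% and 10.8%.
- SDs 0.5 then 1.3, constant correlation 0.4: at week 60 V = 1.402, C = 0.510 and the true variance is 1.42, so r = √(1.785/1.42) = 1.12 and the error is 2.8%.
- Equal SDs of 1.3, correlation 0.6 per 8 weeks: V = 1.69, C = 0.697 and the true variance at week 60 is 3.307, so r = √(1.987/3.307) = 0.78 and the error is 12.9%. With slower decay (0.6, 0.5, 0.4 and 0.2 at gaps of 4, 8, 12 and 48 weeks or more) it is 9.0%. The uneven gaps alone produce this.

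**The case against.** Several points on the other side are sound.

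- **The model is not the only analysis.** Section 10.2 also plans a separate t-test or Mann-Whitney test at each visit, which uses that visit's own spread, and paired or non-parametric tests against baseline. The error rates above belong to contrasts taken from the mixed model, which the protocol does not list one by one. This stands and limits what is at stake.
- **The protocol does not exclude a residual structure.** It names subject as random effect and says no more; an analysis plan that is not shown could add one. That is so, but the model is written out, and fitted as written it is a random-intercept model.
- **Late spread is unknown.** A reader might infer that late-visit standard errors are certainly too small. The documents do not support this. They give no SD after entry, and the remission SD is below the mild one. Protocol 8.4.1 trims high late scores: "A subject will be withdrawn from the study in the case of serious gastro-intestinal complaints or an exacerbation of UC reported by the subjects". With equal SDs the between-arm test at week 60 is correct, and with falling SDs it is conservative. The 0.33 is, however, a spread within one state, so a fall requires nearly all patients to end in the same state.
- **T = 0 is only approximately restricted.** The 3-5 window is applied at screening and P-SCCAI is completed again at baseline.
- **Changes from baseline.** A reader might infer that these are declared significant too often throughout. When SDs widen, the opposite holds at weeks 4 to 12.
- **Other outcomes.** GSRS and SIBDQ are collected only at weeks 0, 4 and 8, so they are little affected. Calprotectin and SCFAs have no entry window, so for them the problem lies mainly in the uneven gaps.

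**Conclusion.** The point holds as a correction to a secondary analysis. The covariance structure implied by 10.2 is implausible for P-SCCAI over these visits, and the model's standard errors are likely miscalibrated, in a direction that depends on visit and contrast.

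For the between-arm difference at week 60, type I error is about 6-8% under mild widening and about 17% if the SD reaches 2.0, against 5% with equal SDs and about 1% if SDs fall. For change from baseline, the tests lose power at weeks 4 to 12 when SDs widen (errors of about 0-3%). At week 60 they run at roughly 3-13%, depending on SDs and on how fast the correlation decays.

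These figures rest on assumed late SDs and correlations, complete data and a fully fitted set of arm-by-visit means. A reader might also infer that the trial's main result is at risk. It is not: the primary week-8 comparison uses a t-test or Mann-Whitney test, and the per-visit tests in 10.2 are equally untouched.

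**What to change.** In 10.2, replace the clause on the random effect with visit as a categorical factor, an unstructured within-subject covariance, REML, and Kenward-Roger or Satterthwaite degrees of freedom. State beforehand a structure with visit-specific variances as the fallback if the model does not converge. Let the outcomes analysed in the same manner refer to this specification.

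Five visits need 5 variances and 10 correlations, 15 parameters in all. Sixty patients start and about 42 are expected to complete (60 × 0.70), so the fit should be feasible, but the fallback is needed.

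The cost is one sentence in the protocol, a few more covariance parameters, and slightly less precision if compound symmetry does hold. The change should be made before unblinding.

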2. OBJECTIVES

Primary Objective:

The primary objective is to validate the prediction that prebiotics intervention boosts butyrate production and thereby induces a higher response (lower mean Patient Simple Clinical Colitis Activity Index (P-SCCAI) score) in mild UC patients with low intestinal Bacteroidetes levels (predicted responders), but not in those with high intestinal Bacteroidetes levels (predicted non-responders) at T = 8 weeks

Secondary Objective(s):

1. To study the effects of the prebiotic intervention on response over time at T = 0, 4, 8, 12, and 60 weeks in mild UC patients
2. To study the effects of the prebiotic intervention on mucosal inflammation (fecal calprotectin levels) in mild UC patients
3. To study the effects of the prebiotic intervention on gastro-intestinal (GI) complaints (e.g., indigestion, abdominal pain) in mild UC patients
4. To study the effects of the prebiotic intervention on stool consistency and frequency in mild UC patients
5. To study the effects of the prebiotic intervention on the gut microbiota composition and SCFAs profile in mild UC patients
6. To study the effects of the prebiotic intervention on health-related quality of life in mild UC patients
7. To study the effects of the prebiotic intervention on medication use in mild UC patients
8. To study the effects of the prebiotic intervention on safety parameters in mild UC patients

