3. STUDY DESIGN

This study is a double-blind randomized placebo-controlled parallel trial. A summary of the study set-up and workflow is shown in **Figure 3**.

[figure not shown]

Figure 3 PREDUCTOME study: set-up and workflow

The study consists of the screening, intervention, and the follow-up periods.

During the **screening** period, approximately one hundred and seventy-seven UC patients will be recruited. P-SCCAII score data will be collected to select mild UC patients which is defined as 3-5 points on a 19-point scale. A stool sample will also be provided by patients to determine the Bacteroidetes level by quantitative polymerase chain reaction (qPCR) quantification of the number of total bacteria and Bacteroidetes. Based on the baseline microbiota from a subject in a fecal microbiota transplantation trial [20], in which healthy donors, sustained responding UC patients, and non-responding UC patients had an average relative abundance of 8%, 5%, and 19% Bacteroidetes, respectively, predicted responders are defined as UC patients having with a relative abundance of Bacteroidetes <=10% in their feces, while predicted non-responders are defined as UC patients with a relative abundance of Bacteroidetes >=15% in their feces. A total of sixty screened mild UC patients will continue with this study that consists of thirty predicted responders and thirty predicted non-responders.

To assess the habitual dietary intake of the last month, a validated food frequency questionnaire (FFQ, see F1) will be taken at the baseline. The data will also be used for potential correlation analysis with other parameters as diet is considered an important modulator of the intestinal microbiota. For the intervention, at **baseline**, selected participants

need to fill out several questionnaires including P-SCCAI (once), gastrointestinal symptom rating scale (GSRS, once), stool consistency (Bristol stool scale, daily for 7 consecutive days), stool frequency (daily for 7 consecutive days), short inflammatory bowel disease questionnaire (SIBDQ, once). Information of medication use and adverse events will be extracted from patient record and diary. In addition, they have to collect a stool sample for determining calprotectin level, microbiota composition, and SCFAs profile.

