8.1.2 Secondary study parameters/endpoints

Response over time

In addition to week 8, subjects need to fill out the P-SCCAI questionnaire at T = 0, 4, 12, and 60 weeks to determine the response over time. Comparisons will be made between groups as well as within subjects over time. With P-SCCAI score <= 2 being regarded as clinical remission, and a decrease in the P-SCCAI score by more than two points from baseline being regarded as clinical response [30, 31, 55] (see F1). We will also determine whether subjects have reached clinical remission and/or showed a clinical response over time.

Mucosal inflammation

At T= 0, 8, 12, and 60 weeks, a fecal sample will be provided by subjects for calprotectin measurement.

GI complaints: (e.g. abdominal pain, bloating, flatulence)

At T= 0, 4, and 8 weeks, the GI complaints will be assessed by the GSRS questionnaire. The GSRS contains 15 items clustered into five domains (reflux, abdominal pain, indigestion, diarrhea and constipation) addressing different gastrointestinal symptoms [56]. It has a seven-point graded scale where 1 represents the absence of troublesome symptoms and 7 represents very

troublesome symptoms (see F1). The reliability and validity of the GSRS are well-documented, and norm values for a general population are available [57].

Stool consistency and frequency

At T = 0, 4, and 8 weeks, subjects will be asked to keep diaries to record stool frequency (bowel movement per day) and consistency of each stool using Bristol stool form scale (see F1) on a daily basis for 7 days.

Gut microbiota and SCFAs: (e.g. microbiota composition, SCFAs profile)

At T = 0, 8, 12, and 60 weeks, a fecal sample will be provided by subjects for 16S rRNA gene-based microbiota profiling and SCFAs measurement. Subsequent analyses of a variety of microbial ecological characteristics, including microbiota composition, α -diversity (diversity within the sample), β -diversity (diversity between the samples), population dynamics over time, and group differences will also be conducted.

Health-related quality of life

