16S rRNA gene sequencing provides sequence read counts data. It will be normalized to microbial relative abundance, and microbiota diversity indices (Shannon, Simpson, and inverse Simpson) are calculated at amplicon sequence variant (ASV) level, as implemented in the Picante [66] and Phyloseq [67] packages in R, respectively. Wilcoxon test will be applied to determine whether diversity as well as the relative abundance of specific bacterial taxa, were significantly different between groups since the data was non-parametric. For microbiota analysis, *p*-values will be corrected for multiple comparisons using the Benjamini–Hochberg procedure. To correct for a false discovery rate (FDR), a FDR adjusted *p*-values will be computed, a so-called *q*-value [68]. A corrected *q*-value of less than 0.2 was considered significant. Paired tests will be used to

compare the effects of prebiotics. Pairwise weighted UniFrac [69] and unweighted UniFrac [70] distance-based principle coordinate analysis (PCoA) will be used to visualize microbial community variation at the ASV level. Permutational multivariate analysis of variance (PERMANOVA) will be used to test for significant differences between groups, as implemented in the Vegan package [71].

Health-related quality of life

Data from SIBDQ will be computed into scores, and the score of each item will be pooled together as the sum score, and the score of each item within each domain will be pooled as well. All data will be analysed in the same manner as described above (Response over time).

Medication use

Type, Dose, frequency and duration of each medication use will be collected. All data will be analysed in the same manner as described above (Response over time).

Safety parameters

Incidence rate of each adverse event is recorded and calculated. All data will be analysed in the same manner as described above (Response over time).

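### The prebiotic effect on the 16S data is assigned to paired tests with no placebo contrast, while the between-group 16S tests are valid but ignore the T=0 sample and lose power

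*Protocol*

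**What the plan says.** The fifth secondary objective (section 2) is "To study the effects of the prebiotic intervention on the gut microbiota composition and SCFAs profile in mild UC patients". Section 3 gives the design: "This study is a double-blind randomized placebo-controlled parallel trial". Section 8.1.2 supplies the data: "At T = 0, 8, 12, and 60 weeks, a fecal sample will be provided by subjects for 16S rRNA gene-based microbiota profiling and SCFAs measurement".

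Section 10.2, under Gut microbiota and SCFAs, names three inferential procedures for the 16S data:

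- For diversity and single taxa: "Wilcoxon test will be applied to determine whether diversity as well as the relative abundance of specific bacterial taxa, were significantly different between groups".
- For the intervention itself: "Paired tests will be used to" "compare the effects of prebiotics".
- For community composition, PERMANOVA, which "will be used to test for significant differences between groups, as implemented in the Vegan package".

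The same section describes a linear mixed model under Response over time, with treatment, predicted-response group, time point and their three-way interaction as fixed effects and subject as random effect. The SCFAs are sent to it: "Fecal SCFAs data will be analysed in the same manner as described above (Response over time"). Calprotectin, GSRS, stool data and SIBDQ are sent there too. The 16S data are not.

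**The concern.** The only sentence that speaks of the effects of prebiotics on the microbiota uses a test without a placebo comparison. Each subject receives one product only, so pairing can only mean before against after. The microbiota may shift over eight weeks for reasons unrelated to the supplement, such as diet, season or the course of the disease. A within-arm paired test cannot separate such a shift from an effect. The placebo arm is there to do so.

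The two between-group procedures have a different and milder weakness. As worded, neither has a baseline term, a change score or a treatment-by-time term. The stable differences between people stay in the error variance, although every arm gives a T=0 sample.

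The trial's rationale is that the intervention acts through the microbiota, so readers will take the 16S results as mechanistic evidence.

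**Working it through.** **Inputs.** From the protocol, section 4.4: two-sided α = 0.05, power 0.90, means 3.5 and 2.8, SD 0.5, 11 evaluable and 15 enrolled per group. The documents give no figure for microbiota drift, effect size or the correlation between baseline and week 8. These are assumptions below and are shown as ranges.

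**The plan's own figure.** n = 2 × [(1.960 + 1.282) × 0.5 / 0.7]² = 10.7, so 11 per group, as stated. It concerns P-SCCAI. It is used here only because 11 to 15 per arm is the number available for the 16S tests.

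**Check 1: paired test, no treatment effect, both arms drifting alike.** Let δ be the drift in SDs of the within-subject change. The paired t-test has noncentrality δ√n on n − 1 degrees of freedom. For example, δ = 0.5 gives 0.5 × √11 = 1.66 and 0.5 × √15 = 1.94. The signed-rank column is simulated. Each cell runs from n = 11 to n = 15, at raw p<0.05.

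| Shared drift δ | Paired t-test, significant | Signed-rank test, significant |
|---|---|---|
| 0 | 5% | 3-5% |
| 0.2 | 9-11% | 7-10% |
| 0.3 | 15-19% | 12-19% |
| 0.5 | 32-44% | 29-42% |

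A rank-sum test of change, prebiotics against placebo, stayed at 3-5% in the same settings. Running the paired test in both arms and reading significant on prebiotics but not on placebo as an effect is no remedy. With no treatment effect, that pattern arose in about 12-25% of simulations (drift 0.3-0.5 SD of the level, correlation 0.5-0.7).

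**Check 2: between-group test at week 8 under the same shared drift.** Drift adds the same amount to both arms and cancels. In simulation this test was significant in 4-5% of cases. It is not biased.

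**Check 3: power of the between-group test.** Effect 0.8 SD, 15 per arm, correlation ρ between T=0 and T=8. Noncentralities:

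- Week 8 only: 0.8 × √(15/2) = 2.19.
- Change score: 2.19 / √[2(1 − ρ)].
- Adjusted for T=0: 2.19 / √(1 − ρ²).

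| ρ | Week 8 only | Change score | Adjusted for T=0 | Variance, week 8 only ÷ adjusted = 1/(1 − ρ²) |
|---|---|---|---|---|
| 0.3 | 56.2% | 43.2% | 60.2% | 1.10 |
| 0.5 | 56.2% | 56.2% | 68.5% | 1.33 |
| 0.7 | 56.2% | 77.9% | 84.2% | 1.96 |
| 0.8 | 56.2% | 91.7% | 94.1% | 2.78 |

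These are t-test figures. By simulation the rank-sum test that the plan names has about 52% at week 8, and baseline adjustment has 59-94% over the same ρ. At ρ = 0.3 about 4 of those 7 points (56% against 52%) come from using a rank test on normal data, and only the rest from the baseline. At higher ρ the baseline accounts for most of the gain. With 11 per arm the t-test figures are 43% for week 8 only and 47-85% adjusted.

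**The case against.** The strongest reply is that the plan already holds a randomised comparison. A Wilcoxon test or PERMANOVA of prebiotics against placebo at week 8 is valid whatever the drift, and Check 2 confirms this. This part stands. A reader might infer that every 16S result would be contaminated by drift, or that no placebo-controlled 16S comparison is planned. The documents support neither inference. The drift problem belongs to the paired sentence alone, and the between-group tests lose only power. The one qualification is that section 10.2 does not say whether its groups are prebiotics and placebo or predicted responders and non-responders.

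A second reply is that the paired tests may be meant as a supplementary description, with details left to a statistical analysis plan that is not shown. That intention is possible, but the text attaches the effects of prebiotics to these tests. It also sends the SCFAs, and not the 16S data, to the mixed model. This is a stated choice of method and not an omitted detail.

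A third reply is that the error rates rest on assumed drift and on raw p<0.05, whereas the plan uses Benjamini-Hochberg with q below 0.2. This is correct, and the figures do not describe the final decision rule. The correction does not cure the fault, because it works on p-values from a test of no change over time and not of no difference from placebo.

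A reader might also infer that a raw change score should replace the week-8 test. Check 3 shows that this loses power when the correlation is below 0.5.

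**Conclusion.** The point holds for the 16S data. The paired tests named for the prebiotic effect have no placebo contrast. Under an assumed shared drift of 0.2 to 0.5 SD of the change they would be significant in about 7-42% of taxa with no effect present, against about 5% for change compared with placebo. With no drift the excess disappears. Separately, the between-group tests are sound as randomised contrasts but discard the T=0 sample. For a 0.8 SD effect at 15 per arm this means about 52% power against 59-94% with baseline adjustment, for a correlation of 0.3 to 0.8. The loss is small at the low end of that range and large at the high end.

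The scope is limited. The SCFAs, butyrate included, have the mixed model. The 16S analysis serves a secondary objective, and nothing here touches the P-SCCAI endpoint or the sample size. The change is worth making before unblinding.

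**What to change.** In section 10.2, make the test of the prebiotic effect on the diversity indices and on suitably transformed taxa a prebiotics-versus-placebo comparison adjusted for the T=0 value. Alternatively, extend the mixed model under Response over time to these data and read the treatment-by-time contrast within each predicted-response group. Either way:

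- keep the samples at weeks 0, 8, 12 and 60;
- keep the contrast of predicted responders with predicted non-responders, and say which groups each between-group test compares;
- keep the Benjamini-Hochberg correction across taxa;
- state that within-arm paired tests are descriptive and not evidence of a prebiotic effect.

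The cost is a few lines of wording and slightly more analysis work, including a transformation for skewed taxa. No extra sample, visit or subject is needed, because all arms already provide the T=0 and later samples.
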